14.2 Schedule of Activities

Visit	Screening	Vis Da	it 1/ y 1	Vis We	it 2/ ek 6	Safety Follow-up 1 ^j	Safety Follow-up 2 (EOS) j	Early Termination (ET) ^{k,l}
Window	Day -30 to Day 1	± 0	days	Week 6 t	o Week 8	1-3 Days After Visit 2	28 (± 3) Days After Visit 2	<7 days from ET Decision
Timing of Activity(ies)		Prior to 124I-AT-01	124I-AT-01 and Scan	Prior to 124I-AT-01	124I-AT-01 and Scan			
Assessment/Procedures								
Informed Consent a	X							
Medical history and Demographics	X							
Inclusion and Exclusion criteria	X							
Concomitant Medications	X	X	X	X	X	X	X	X
Oral Potassium Iodide (KI) b		X		X				
¹²⁴ I-AT-01 Administration ^c			X		X			
Biomarker and Safety Assessments								
Vital Signs (HR and BP) d		X	X	X	X			
Body Weight		X		X				
Height		X						
Pregnancy Test (WOCBP) e,f	X			X				
PET/CT Scan			X		X			
Adverse events g	X	X	X	X	X	X	X	X
Laboratory h,i	X			X		X		
Biomarkers h,i	X			X				
Urine UACR (AL subjects only) i	X			X				
Serum ADA i	X			X			X	X

All sections in blue refer to protocol sections:

Abbreviations: ADA = anti-drug antibodies; AL = amyloid light chain amyloidosis; BP = blood pressure; CBC = complete blood count; EOS = end of study; ET = early termination; HR = heart rate; NT-proBNP = N-terminal prohormone of brain natriuretic peptide; UACR = urine albumin-to-creatinine ratio; WOCBP = women of childbearing potential.

- a. Informed consent, as described in Section 10.1.3.
- b. KI is self-administered by the subject daily for 3 days, beginning >30 minutes and <24 hr prior to dosing, as described in Section 4.1.2.
- c. ¹²⁴I-AT-01 will be administered by IV infusion over 2-5 minutes (protocol Version 1.1) or slow IV bolus at 1 mL/5 seconds (protocol Version 2.0), as described in Section 4.1.3. For all subjects, ¹²⁴I-AT-01 will be administered by the same route (IV infusion over 2-5 minutes or slow IV bolus at 1 mL/5 seconds) at the Week 6 visit as on the Day 1 visit.
- d. Subjects must remain semi-recumbent for at least 5 minutes prior to blood pressure measurements. Blood pressure and heart rate will be measured within an hour prior to dosing and 5-10 minutes after administration of ¹²⁴I-AT-01.
- e. Serum pregnancy test, as indicated in Section 10.2, will be obtained in all women of childbearing potential.
- f. Serum pregnancy and all other laboratory samples must be drawn within 7 days prior to administration of ¹²⁴I-AT-01 in all WOCBP. The results of the pregnancy test must be available and be negative prior to ¹²⁴I-AT-01 administration in all WOCBP.
- g. Adverse events will be monitored from Screening through the EOS Visit. For Safety Follow-up 1 and 2, adverse events and concomitant medications can be obtained by phone call.
- h. Clinical laboratory tests and biomarker analysis, as described in Section 10.2. Baseline sample will be collected within 30 days prior to the first administration of ¹²⁴I-AT-01; second sample within 7 days prior to the second administration of ¹²⁴I-AT-01; third sample at Safety Follow-up 1 after the second administration of ¹²⁴I-AT-01.
- Urine and blood may be collected locally by visiting nurse/phlebotomist. An additional serum ADA sample will be obtained at Screening for subjects who provided consent for the extra ADA sample.
- j. Safety follow-ups for concomitant medications and adverse events will be done via telephone call for all subjects. Both Safety Follow-up 1 and Safety Follow-up 2 activities will be conducted for subjects who discontinue for IRRs at either the first or second administration of ¹²⁴I-AT-01.
- k. Blood draw for ADA should be obtained if ET is ≥4 weeks after first administration of ¹²⁴I-AT-01.
- Early Termination activities do not apply to subjects discontinued for IRRs. Please follow Safety Follow-up 1 and Safety Follow-up 2 activities for subjects experiencing IRR with either the first or second administration of ¹²⁴I-AT-01.

Page 31 of 38

14.3 Clinically Significant Change in Laboratory Values and Vital Signs

Category	Measurement	Criteria for Clinically Significant Change
Laboratory	Hematocrit (%)	Decrease > 20% and < LLN
_		<pre>Increase > 20% and > ULN</pre>
Laboratory	Hemoglobin (g/dL)	Decrease > 20% and < LLN
_		<pre>Increase > 20% and > ULN</pre>
Laboratory	Leukocytes (x109/L)	Decrease > 20% and < LLN
		<pre>Increase > 50% and > ULN</pre>
Laboratory	Lymphocyte count $(x10^9/L)$	Decrease > 20% and < LLN
		<pre>Increase > 50% and > ULN</pre>
Laboratory	Neutrophils $(x10^9/L)$	Decrease > 20% and < LLN
		Increase > 50% and > ULN
Laboratory	Platelets (x10 ⁹ /L)	Decrease > 20% and < LLN
		Increase > 50% and > ULN
Laboratory	Glucose (mmol/L)	Value < 2.775 mmol/L
		Increase > 50% and > ULN
Laboratory	Bilirubin (umol/L)	Increase > 50% and > ULN
Laboratory	Alkaline phosphatase (IU/L)	Increase > 50% and > ULN
Laboratory	Aspartate Aminotransferase (IU/L)	Increase > 100% and > ULN
Laboratory	Alanine Aminotransferase (IU/L)	<pre>Increase > 100% and > ULN</pre>
Laboratory	Potassium (mmol/L)	Absolute decrease $>$ 0.8 mmol/L and $<$
		LLN
		Absolute increase > 0.8 mmol/L and >
		ULN
Laboratory	Sodium (mmol/L)	Absolute decrease > 0.8 mmol/L and <
		LLN
		Absolute increase > 0.8 mmol/L and >
		ULN
Vital Signs	Systolic Blood Pressure (mmHg)	Decrease > 20 mmHg and SBP < 90 mmHg
Vital Signs	Diastolic Blood Pressure (mmHg)	Increase > 10 mmHg and DBP < 50 mmHg

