5.2 Exclusion Criteria

Subjects are excluded from the study if any of the following criteria apply:

- 1) Is pregnant or breast-feeding.
- 2) Is mentally or legally incapacitated, has significant emotional problems at the time of the study, or has a history of psychosis.
- 3) Has received in the last 6 months or are currently receiving treatment with anti-amyloid monoclonal antibody therapy (i.e., CAEL101, NEOD001, PRX-004, or NI006) or are expected to begin treatment prior to completing this study.

- 4) Has received heparin or heparin analogs (e.g., enoxaparin, dalteparin, fondaparinux) within 7 days of Day 1 (first administration of ¹²⁴I-AT-01).
- 5) Has a significant co-morbidity (e.g., ECOG score of 3 or greater), NYHA Class IV heart failure, uncontrolled infection, or other ongoing serious illness.
- 6) Has a known allergy to potassium iodine treatment.
- 7) Has end-stage renal disease and is receiving hemodialysis or peritoneal dialysis.
- 8) Has severe claustrophobia that would prevent completion of the PET/CT imaging protocol.
- 9) Has received an investigational agent within five half-lives of the agent or 30 days, whichever is longer, prior to Screening.
- 10) Has any illness that, in the opinion of the Investigator, might confound the results of the study or pose additional risk to the subject.

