10.2 Appendix 2: Clinical Laboratory Tests

| Laboratory Tests | Parameters | | | | |
|----------------------|---|-----------------|--|---|--|
| Hematology | Complete blood count (CBC) with differential | | | WBC differential: Bands/stabs Neutrophils Eosinophils Basophils | |
| | White blood cell (WBC) count | | | | |
| | Red blood cell (RBC) count | | | | |
| | Hemoglobin (Hgb) | | | | |
| | Hematocrit (Hct) | | | Lymphocytes | |
| | Platelet count (Plt) | | | • Monocytes | |
| Serum Chemistry | Sodium (Na) | Creatinine (Cr | ·) | Alanine aminotransferase (ALT, SGPT) | |
| | Potassium (K) | Uric acid | | Aspartate aminotransferase (AST, SGOT) | |
| | Chloride (Cl) | Albumin | | Calcium (Ca) | |
| | Bicarbonate (HCO ₃)/CO ₂ | Total protein | | Phosphate (PO ₄) | |
| | Glucose | Total bilirubin | 1 | Lactate dehydrogenase (LDH) | |
| | Blood urea nitrogen (BUN) | Alkaline phos | phatase | | |
| Biomarker Assays | N-terminal prohormone of brain natriu peptide (NT-proBNP) | | Serum free light chain ¹ | | |
| | Brain natriuretic peptide (BNP) | | Urine albumin creatinine ratio (UACR) ¹ | | |
| Pregnancy Testing | Highly sensitive serum human chorionic gonadotropin (hCG) pregnancy test (as needed for women of childbearing potential) ² | | | | |

- Subjects with AL systemic amyloidosis only.
- 2. Serum pregnancy and laboratory tests must be drawn within 7 days prior to ¹²⁴I-AT-01 administration in all WOCBP. The results of the pregnancy test must be available and be negative prior to ¹²⁴I-AT-01 administration in all WOCBP.

- 51 -

Т

10.3 Appendix 3: AEs and SAEs: Definitions and Procedures for Recording, Evaluating, Follow-up, and Reporting

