9.5 Clinical Laboratory Evaluation

Baseline for clinical chemistry parameters is defined as the most recent laboratory measurement obtained prior to the initiation of study drug. The post-baseline visits are Visit 2 / Week 6 and Safety Follow-up 1 (1-3 days after the second infusion).

Baseline and all post-baseline visit values and change from baseline to post-baseline in laboratory parameters for clinical labs will be summarized for the Safety Set using descriptive statistics, as described in Section 4. Unscheduled visits will be mapped to scheduled visits using analysis windows according to Section 8.1.2.

Biomarkers include NT-proBNP, brain natriuretic peptide (BNP), serum free light chains (only subjects with AL amyloidosis), UACR (only subjects with AL amyloidosis), FLC ratio (Kappa/Lambda) (only subjects with AL amyloidosis), and dFLC (only subjects with AL amyloidosis).

Serum chemistry, Hematology, and biomarker assays will also be presented in data listings for subjects in the Safety Set. The listing will include the reference range (if applicable), classification of high, low, critical, or exclusion, and an abnormal flag. Classification of laboratory values and reference ranges in the data listings will be based on the global laboratory reference ranges used across all sites.

Laboratory parameters with clinically significant changes will be summarized and listed as 'flagged' based on the Sponsor's internal guidelines based on Appendix 14.3.

Additional categorizations of biomarker results for the Image Evaluable Set will be produced including the number and percentage of subjects with:

- Screening and Visit 2 NT-proBNP < 650 ng/L
- Screening or Visit 2 NT-proBNP >= 650 ng/L
- Screening or Visit 2 NT-proBNP >= 650 ng/L and change in NT-proBNP of >= 30% and >= 300 ng/L from Screening to Visit 2
- Screening or Visit 2 NT-proBNP missing
- AL subjects with a normal FLC ratio at Screening and Visit 2

This summary will also include descriptive statistics for dFLC in AL subjects with an abnormal FLC ratio at Screening or Visit 2. NT-proBNP will be displayed in ng/L using the conversion: 1 ng/L = 8.457 pmol/L.Pregnancy test results will also be presented in a data listing for the Safety Set.

Page 24 of 38

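### The SAP's criteria for clinically significant laboratory changes include no renal-function measure, so a marked creatinine rise would not be counted as such in Table 14.3.3.4

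*SAP*

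**What the plan says.** SAP 9.5 states: "Laboratory parameters with clinically significant changes will be summarized and listed as 'flagged' based on the Sponsor's internal guidelines based on Appendix 14.3". The resulting display is Table 14.3.3.4, on the Safety Set. Protocol 9.5.4 adds that flagged parameters are reported by incidence and frequency.

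Appendix 14.3, "Clinically Significant Change in Laboratory Values and Vital Signs", under the column "Criteria for Clinically Significant Change", has rows for:

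- six haematology measures: hematocrit, hemoglobin, leukocytes, lymphocytes, neutrophils and platelets;
- seven chemistry measures: glucose, bilirubin, alkaline phosphatase, AST, ALT, potassium and sodium;
- two blood-pressure measures.

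Protocol Appendix 2 puts creatinine and BUN in the serum chemistry panel and UACR (AL subjects only) among the biomarkers. The Schedule of Activities places the laboratory panel at Screening, Visit 2 and Safety Follow-up 1, and UACR at Screening and Visit 2.

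On the population, Protocol 5.1 lets an AL subject meet the organ-involvement criterion through a positive renal biopsy, 24-hour urine protein or UACR. The exclusion specific to kidney disease in Protocol 5.2 is: "Has end-stage renal disease and is receiving hemodialysis or peritoneal dialysis". SAP 6.2 defines a CKD-EPI formula for eGFR and a separate FLC-ratio range for subjects with eGFR below 30. SAP 8.2 names kidney as one of the four organs in the primary analysis.

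**The concern.** Appendix 14.3 works as a closed list. A programmer who follows it will produce Table 14.3.3.4 without a creatinine, BUN, eGFR or UACR line, whatever the data show. Liver function has four criteria and renal function none, in a trial that enrols subjects with renal amyloid and analyses the kidney.

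Change from baseline in laboratory values is a secondary endpoint. With about 20 subjects and no hypothesis test, the useful safety question is how many individuals had a marked change. Table 14.3.3.4 is the only planned laboratory display that answers this with a fixed numerical rule, and it cannot answer it for the kidney. SAP 9.5 does add rule-based categories for NT-proBNP and the FLC ratio, but none for a renal marker.

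**Working it through.** The plan states no figure to reproduce. The check compares two lists, tests each alternative display, and uses a short illustration for scale.

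**1. Analytes measured against analytes with a criterion** (Protocol Appendix 2 against SAP Appendix 14.3, pregnancy test left out)

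| Group | Measured | With a criterion |
|---|---|---|
| Haematology, including differential | 11 | 6 |
| Serum chemistry | 17 | 7 |
| Biomarkers | 4 | 0 |
| Total | 32 | 13 |

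The 32 − 13 = 19 without a criterion include creatinine, BUN, uric acid and UACR. Renal-function criteria: 0. Potassium and sodium appear as electrolytes.

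**2. Scale of a change that meets no criterion.** SAP 6.2 formula for an assumed 70-year-old man without the race term, creatinine at or above 0.9 mg/dL:

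eGFR = 141 × (SCr/0.9)^(−1.209) × 0.993^70

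- SCr 1.0: 141 × 0.880 × 0.612 = 75.9
- SCr 2.0: 141 × 0.381 × 0.612 = 32.8

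At a lower baseline, where the formula's exponent −0.411 applies below 0.9, a rise from 0.5 to 1.0 mg/dL takes eGFR from 109.8 to 75.9. Neither doubling meets a row of Appendix 14.3.

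**3. What the other displays would show**

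- *Chemistry listing (16.2.8.1).* It gives the reference range, a high/low/critical class and an abnormal flag for each value. The first doubling would probably be marked high and the second might not be. This is an assumption, because the documents give no creatinine range. A subject whose creatinine is already high at baseline would carry the same mark with or without a further rise.
- *Change-from-baseline summary (Table 14.3.3.1).* SAP Section 4 requires mean, SD, minimum, maximum, median and n. Suppose 1 of 20 subjects changes by +1.0 mg/dL and the others by 0. Then the mean is 1.0/20 = 0.05, the SD is √[(0.95² + 19 × 0.05²)/19] = √0.05 = 0.22, and the maximum is +1.0. The outlier is visible.
- *What that summary cannot show.* If 2 of 20 change by +1.0, the maximum is still +1.0 (mean 2.0/20 = 0.10). A maximum of +1.0 could be a doubling from 1.0 or a one-third rise from 3.0 (1.0/3.0 = 33%). Neither the number of subjects nor the relative change can be read from it.
- *Adverse events.* Protocol Appendix 3 counts a worsened laboratory result as an AE if the investigator judges it clinically significant. It leaves out findings associated with the underlying disease unless they are more severe than expected.

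None of these gives a count of subjects by a fixed rule.

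**The case against.** The strongest reply is that the data are not lost. Creatinine is listed by subject with an abnormal flag, its extremes are tabulated, and clinically important worsening can be an AE. This stands, and it limits the point.

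A reader might infer that a renal injury has no chance of being flagged, or that the group mean would conceal it. The documents support neither. The listing has its own flag, the planned maximum and SD expose a single outlier, and a renal injury with a potassium rise large enough for the potassium row would enter Table 14.3.3.4 by that route.

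Two further inferences also fail:

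- *That eGFR is derived only at baseline.* The SAP does not say so. Its FLC-ratio limits depend on eGFR, and SAP 9.5 classifies that ratio at Visit 2, which may require a Visit 2 value.
- *That dialysis is the only renal ground for exclusion.* Protocol 5.2 also allows exclusion for significant co-morbidity, other serious illness, or an illness that adds risk in the investigator's opinion. Subjects with low eGFR can enter, but not without restriction.

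The reply can add that no text promises a criterion for every analyte, that the sponsor's internal guidelines are not visible, and that Protocol 2.2.2 reports no drug-related serious adverse events in the earlier study. All true: there is no contradiction between documents and no known renal signal. But the SAP names Appendix 14.3 as the basis for flagging, and neither document explains why renal function is absent.

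**Conclusion.** The point holds in a limited form. As written, Table 14.3.3.4 cannot count a doubling of creatinine as a clinically significant creatinine change, because 0 of its 13 laboratory criteria concern renal function. The loss is one rule-based subject count in a descriptive summary of a secondary endpoint. The primary repeatability analysis is unaffected and no conclusion is invalidated.

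The comparison of the two lists needs no assumption. The eGFR figures assume a 70-year-old man without the race term, and the mean, SD and maximum assume 20 subjects of whom 19 are unchanged. The change is worth making because this population can include renal amyloid, where a creatinine rise may be attributed to underlying disease and so not reported as an AE.

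**What to change.** Before database lock:

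1. Add a creatinine row to SAP Appendix 14.3 and Table 14.3.3.4, as a reporting flag only. The form already used for bilirubin, alkaline phosphatase, AST and ALT (a relative increase together with a value above ULN) would fit the table. The sponsor should set the cut-off. If no renal criterion is wanted, state why.
2. Summarize eGFR and its change from baseline at Visit 2 and Safety Follow-up 1, using the SAP 6.2 formula. This complements the flag, because a large relative rise from a low baseline could stay below ULN.

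The cost is one appendix row and a few derived values from creatinine already drawn, with no new samples or visits. The downside is a few more flags in subjects with unstable chronic renal disease. The by-subject listing lets a reader put these in context.

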9.3 Sample Size Determination

A formal sample size calculation is not provided for this study. The sample size of up to 20 subjects was estimated based on systematic literature review analysis sets.

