9.5.4 Safety Analysis

Safety will be assessed through reported adverse events (graded using NCI CTCAE version 5) and changes in laboratory parameters.

Adverse Events

All adverse events occurring during the study will be recorded and classified based on Medical Dictionary for Regulatory Activities (MedDRA) terminology. Only treatment-emergent adverse events (TEAEs), which are adverse events that occur after the start of study drug, will be summarized.

The number and percentage of subjects experiencing TEAEs and SAEs will be tabulated for the safety population by system organ class (SOC) and preferred term (PT). TEAEs and SAEs will be tabulated by severity and relationship to study medication. Each subject will be counted only once within a SOC or a PT by using the AE with the highest severity or greatest relationship, respectively, within each category.

TEAEs or SAEs leading to early discontinuation will be summarized as described above. Treatment-emergent adverse events starting on the day of dosing at each dosing visit will be summarized by SOC and PT to evaluate potential infusion-related reactions.

Listings for all reported adverse events, including SAEs, will be provided. In addition, separate listing for SAEs, AEs leading to premature withdrawal from the study, and all deaths will be generated.

Vital signs will include blood pressure (mmHg) and heart rate (beats per minute). Vital signs will be summarized at Baseline and for each study visit when vital signs were obtained. Changes from Baseline in vital sign measurements will also be summarized. Baseline is defined as the last vital signs obtained prior to the initiation of study drug.

Clinical Laboratory Analyses

Baseline for clinical chemistry parameters is defined as the most recent laboratory measurement obtained prior to the initiation of study drug. Clinical laboratory parameters from the tests itemized in Section 10.2, will be summarized as both absolute value and change from Baseline for each visit per the SoA (Section 1.3).

Laboratory parameters with quantitative abnormalities will be listed as 'flagged' based on the Sponsor's internal guidelines. Flagged laboratory parameters will be presented by incidence and frequency.

Clinical safety laboratory tests performed during the study will be analyzed by a central clinical laboratory.

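### SAP 14.3 gives sodium the same 0.8 mmol/L change as potassium, so for a subject with normal baseline sodium the flag means little more than newly out of range

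*SAP*

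**What the plan says.** SAP 14.3 sets the criteria. For both potassium and sodium, a low flag is "Absolute decrease $>$ 0.8 mmol/L and $<" LLN and a high flag is "Absolute increase > 0.8 mmol/L and >" ULN. (The dollar signs come from the PDF text; the two rows state the same rule.) These are the only laboratory rows that use an absolute change. The remaining two-part laboratory rows use a relative change plus an out-of-range value, for example "Decrease > 20% and < LLN" for haemoglobin, rising to 50% or 100% for other analytes.

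SAP 9.5 states the use: "Laboratory parameters with clinically significant changes will be summarized and listed as 'flagged' based on the Sponsor's internal guidelines", with a reference to the 14.3 table. Protocol 9.5.4 adds: "Flagged laboratory parameters will be presented by incidence and frequency". The output is Table 14.3.3.4. Neither document gives a sodium reference range (SAP 9.5 refers only to "global laboratory reference ranges used across all sites"), a reporting precision for sodium, or a reason for 0.8 mmol/L.

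**The concern.** A two-part rule of this kind is meant to pick out values that are both abnormal and substantially changed. The change condition should remove values that drift across a limit through ordinary variation. Sodium circulates at roughly 30 times the concentration of potassium (about 140 against 4.25 mmol/L, both assumed), so a change that is demanding for potassium is trivial for sodium. A programmer will code the row as written, since SAP 2 puts the SAP above the protocol where the two differ.

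At stake is the meaning of one label. Change in clinical laboratory values is a secondary endpoint. In a study of up to 20 subjects, a few sodium entries in a table of clinically significant changes would draw attention, although they had met a much weaker test than the potassium entries beside them.

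**Working it through.** The plan states no rate for this flag, so there is no figure to reproduce. I made three checks.

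**Inputs from the documents.** The rule is in SAP 14.3. Protocol 9.3 plans up to 20 subjects. SAP 9.5 has two post-baseline laboratory visits, Visit 2 and Safety Follow-up 1, so there are at most about 20 × 2 = 40 post-baseline sodium values. The table does not name the reference point for change; I take it as baseline, as in SAP 9.5.

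**Inputs assumed.** Sodium range 135-145 mmol/L (also 136-145 and 133-146); potassium range 3.5-5.0 mmol/L; sodium reported to 0 or 1 decimal; means and SDs as listed below.

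**1. Scale of 0.8 mmol/L.**
- Potassium: 0.8/5.0 = 16.0% to 0.8/3.5 = 22.9%.
- Sodium: 0.8/145 = 0.55% to 0.8/135 = 0.59%.

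**2. Whole-number sodium, all baseline/post-baseline pairs from 120 to 160.** A change above 0.8 is then the same as any change of at least 1.
- Newly out of range, limits 135-145: 11 in-range baselines × 30 out-of-range values = 330 pairs, of which 330 are flagged. For 136-145: 10 × 31 = 310, all flagged. For 133-146: 14 × 27 = 378, all flagged. A threshold of 0 would flag the same pairs.
- Already low and still low, limits 135-145: 15 × 15 = 225 pairs. Those that fall further number 15 × 14/2 = 105, and only these are flagged.

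**3. Simulation with no true change** (1,000,000 baseline/post-baseline pairs per setting, limits 135-145). Each subject has a fixed true sodium level, and each visit adds independent noise. Expected count = 40 × flag rate.

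| Mean | SD between subjects | SD at each visit | Whole mmol/L: rate, count in 40 | One decimal: rate, count in 40 |
|---|---|---|---|---|
| 140 | 2 | 1 | 1.03%, 0.41 | 1.42%, 0.57 |
| 140 | 2.5 | 1.5 | 4.41%, 1.76 | 5.44%, 2.18 |
| 139 | 2.5 | 1.5 | 5.30%, 2.12 | 6.41%, 2.56 |
| 139 | 3 | 2 | 10.27%, 4.11 | 11.72%, 4.69 |

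A lower-sodium population (mean 137, SD 2 between subjects, SD 2 at each visit, whole mmol/L) gives about 5.5 low-sodium flags in 40. One-decimal reporting or more visit noise takes that setting above 6 (about 6.6 at a visit SD of 2.5). The range 0.4 to 5.5 is therefore an illustration and not a bound.

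In the four tabulated settings with one-decimal reporting, 86-96% of newly out-of-range values are flagged, so the 0.8 screens out only 4-14% of them. Across both precisions, 59-75% of all out-of-range sodium values are flagged. The same 0.8 rule flags 2-13% of out-of-range potassium values (assumed mean 4.25, SD 0.30-0.35 between subjects, 0.2-0.3 at each visit).

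**The case against.** Several stronger readings are tempting, and the documents do not support them.

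- *The change criterion is empty.* It is not. A subject already out of range who is stable or improving is not flagged: 120 of the 225 already-low pairs escape, and so do 25-41% of out-of-range values in the simulation. Only the size requirement falls away, and fully so only for whole-number reporting.
- *Every other row in the table uses a relative change.* The blood pressure rows use absolute changes in mmHg, and low glucose is a fixed value with no change condition. The contrast holds only against the other two-part laboratory rows.
- *This is a proven copying slip.* The identical number suggests one, but SAP 9.5 bases the flags on an internal sponsor guideline that is not in the documents. A deliberate rule to show newly abnormal sodium cannot be excluded.
- *A particular replacement follows.* It does not. Carrying the 20% rule over would give 0.20 × 140 = 28 mmol/L, while a figure such as 5 mmol/L is 5/140 = 3.6% and has no source in the plan.

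The case for regarding this as minor also has weight. Only values that really are out of range can be flagged, so the rule lists too much and hides nothing. Table 14.3.3.4 is one of several laboratory outputs: SAP 9.5 also provides descriptive values, changes from baseline and by-subject listings with reference ranges. Abnormal results become adverse events through the investigator's judgement (Protocol 10.3.1), not through this flag. At the high end of the simulation, with mean 137 and SD 2, about 16% of subjects have a true sodium below 135; their flags reflect no change, but they are not healthy subjects. These points limit the consequence. They do not explain why adjacent rows under one label should apply such different tests.

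**Conclusion.** The point stands in limited form. As written, the sodium row does not apply the large-change condition that the other two-part laboratory rows apply. For an in-range baseline it reduces to newly out of range (exactly so in whole mmol/L, nearly so at one decimal), and for an out-of-range baseline to moved further out. The scale mismatch, 16-23% against about 0.6%, depends only on conventional reference ranges that I have assumed. The expected yield with no true change, roughly 0.4 to 5.5 flags in about 40 values, depends on the assumed limits, precision, mean and variability, and should be read as an order of magnitude. The effect is confined to a descriptive safety table; neither the repeatability analysis nor any treatment decision depends on it.

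**What to change.** Before Table 14.3.3.4 is run, the sponsor should compare the sodium row of SAP 14.3 with its internal guideline, and then do one of two things.

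- If 0.8 mmol/L is not the intended figure, replace it in both sodium lines with a sodium-specific reporting threshold that exceeds ordinary visit-to-visit variation. The sponsor sets the value. The LLN/ULN condition stays.
- If 0.8 mmol/L is intended, say so with the reason, and label the sodium row as newly or further out of range instead of as a clinically significant change.

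This is a reporting threshold, not a rule for managing subjects. The cost is two cells, or one label, in a SAP appendix, plus the matching line of code. The same check could take in the diastolic row, which pairs a rise in pressure with a low resulting value.
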